# 3.5.3 Sample Size

Over the course of the study, target enrolment is 66 with the goal of 60 completers. Participants will be randomized in a 1:1 ratio to receive one of the following: 120mg Alvelestat (MPH966) BID or placebo. Randomization will be stratified by AAT genotype/phenotype.

The study will be powered for within-individual change in plasma desmosine/isodesmosine (DES) as the primary endpoint at Week 12 compared to baseline. A sample size of 30 participants in the MPH966 treatment group will give us >90% power to detect a 15% mean decrease of plasma DES from baseline to 12 weeks follow-up in patients treated with MPH966 (within subject change) using a two-sided paired t-test at  $\alpha$ =0.05. The calculation is based on an assumed correlation value of 0.5, baseline mean DES value of 0.466 and standard deviation of 0.09. This 15% mean decrease has been observed in trials of standard dose augmentation versus placebo (Ma S, 2013). A recent study of double dose versus single dose augmentation revealed a within subject decrease in plasma DES from 0.42 +/-0.03 ng/ml to 0.38 +/- 0.03 ng/ml (Campos MA, 2019). We will have >99% power to detect a comparable difference in DES in those who have Alvelestat added to augmentation if we assume their observed SD=0.03 and 85% power if we double their assumed SD, i.e., SD=0.06. Power will not be enough (~50%) to detect this difference if we use our original SD value of 0.9.

For comparing the mean change in DES between the two groups (placebo vs. MPH966), and assuming that there is no placebo effect over 12 weeks, a two-sided two sample t-test at  $\alpha$ =0.05 with a sample size of 60 (30 per group) reveals that we will have 82% power to detect a 15% difference in mean change in plasma DES.

By including a 10% attrition rate over 12 weeks, the required sample size is inflated to 66 (33 per group) to achieve the estimated powers. If we observe attrition rate less than we expected, we will have more statistical power to detect the expected differences. As one interim analysis will be conducted only for safety concerns (see Data Safety and Monitoring Plan), no adjustments to the Type I error are considered for estimating statistical powers.

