# 6 General Aspects for Statistical Analyses

# 6.1 General Methods

Database lock will occur once all subjects complete the final study visit (Safety follow up at Week 16) or terminate early from the study. All analyses will be performed after data lock and cleaning. Statistical analysis will be performed using SAS® version 9.4 or higher. The main population for efficacy analysis will be the Full Analysis Set; supportive analyses will also be performed using the Per-Protocol Set.

Continuous data will be presented using descriptive summaries (e.g., mean, standard deviation, minimum, maximum, median, lower quartile, and upper quartile). Categorical variables will be presented by the number of observations and relative (%) frequency.

Unless otherwise stated, baseline value for any variable will be the last value taken prior to the first dose of study medication. In general, all data will be listed, sorted by site, treatment and subject, and when appropriate by visit number within subject. All summary tables will be structured with a column for Active, Placebo and Total, and will be annotated with the total population size relevant to that table/treatment, including any missing observations.

As a Phase II study, no adjustments for Type I errors (see Section 6.6) will be done. All tests will be 2-sided and conducted at the 5% level. Confidence intervals will be 2-sided 95% confidence intervals.

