# 8.1 Primary Efficacy Endpoint Analyses:

The primary outcome is the relative change from baseline at week 12 in plasma desmosine/isodesmosine levels within treatment group. Within individual relative (percent) change from baseline in plasma desmosine/isodesmosine levels will be analyzed using Mixed Model Repeated Measures (MMRM). Relative change (percent) from baseline will be considered the response variable, with time as main independent fixed effect variable and baseline levels, augmentation, age, and smoking history (yes/no) as a fixed effect covariates, using an unstructured covariance matrix to model the within-subject errors. Available data from all time points will be included. The least squared estimates of the mean at each Week and EndPoint will be generated. [Note: Originally, it was planned to use sputum strata and FEV1 as covariates in the model. However, due to the restrictions of the pandemic, there was limited opportunity to collect the required sputum, and therefore will not be included in the analyses.] The analysis will be conducted using the SAS 'proc mixed', with the below specific code:

proc mixed data=Data; by TRTP; class SUBJID TRTP AVISIT AUGMENTATION SMOKING; model PCTCHG = BASE AVISIT AUGMENTATION AGE SMOKING; ddfm=KENWARDROGER; repeated AVISIT/ subject=SUBJID type=UN; lsmeans AVISIT / pdiff; run;

where PCTCHG is the relative (percent) change from baseline, BASE are baselines values, TRT is treatment arm, AVISIT is Weeks, AGE is age at enrollment, SMOKING is yes/no at enrollment and AUGMENTATION (yes/no) at enrollment. If imbalances are found between treatment groups in baseline characteristics deemed to be clinically important in influencing the relative change in the outcome, sensitivity analyses will be performed by including these variables as covariates in the above model. P-value<0.05 for the mean difference at Week 12 will be deemed significant. Estimate including 95% confidence interval of the least squares mean difference will also be provided.

If any issues related to convergence occur and cannot be resolved within the 'proc mixed', then alternative procedures will be considered (such as 'proc glimmix'). Other covariance structures will also be considered if convergence is an issue with unstructured covariance. Transformation of data or alternative distribution for the model will be considered should there be evidence of nonnormality of the data.

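### The primary Week 12 LS mean in SAP 8.1 describes a hypothetical arm that is half augmented and half smokers, not the patients treated, and loses precision when those splits are uneven

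*SAP*

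**What the plan says.** SAP 4.1 and 8.1 define the primary efficacy result as the within-individual percent change in plasma DES, estimated within treatment group. The SAP 8.1 code runs the model by arm and declares "class SUBJID TRTP AVISIT AUGMENTATION SMOKING". Baseline DES, visit, augmentation, age and smoking enter as main effects, with no covariate-by-visit terms. The estimates come from "lsmeans AVISIT / pdiff; run". Neither the code nor the text says at what mix of augmentation and smoking the means are to be evaluated. Significance is judged at Week 12, and SAP 6.1 states "All tests will be 2-sided and conducted at the 5% level".

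SAP 3.5.3 says of the sample size: "A sample size of 30 participants in the MPH966 treatment group" "will give us >90% power to detect a 15% mean decrease of plasma DES", using a two-sided paired t-test. It adds: "The calculation is based on an assumed correlation value of 0.5, baseline mean DES value of 0.466 and standard deviation of 0.09". Neither document gives an expected split for augmentation or smoking. SAP 10 explains that the mixed model over all follow-up visits replaces the Week 12 ANCOVA in the protocol.

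**The concern.** LSMEANS without an observed-margins option averages equally over the levels of each CLASS effect. In an additive comparison between arms this would not matter, because the same weights appear in both means and cancel. Here the primary result is the LS mean of a single arm, so the weights enter its value, its standard error and its test against zero in full.

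Two things are at stake. First, if few treated patients are in one class, half the weight rests on them and the standard error rises. Second, if the change in DES differs by augmentation, the reported mean describes a mix that was not enrolled. That is a live possibility: augmented patients were admitted by amendment, and SAP 6.3 plans a subgroup analysis by augmentation.

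**Working it through.** **1. The plan's own figure.** Inputs from SAP 3.5.3: mean 0.466, SD 0.09, r = 0.5, n = 30, 15% fall, two-sided 5%.
- Fall: 0.15 × 0.466 = 0.0699.
- SD of change: 0.09 × √(2(1 − 0.5)) = 0.09.
- Standardised effect: 0.0699/0.09 = 0.777.
- Noncentral t, 29 df, noncentrality 0.777 × √30 = 4.25: power 98.4%.

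The stated figure above 90% reproduces. When individual percent change is simulated from the same inputs, a paired t-test has about 93% power.

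**2. What equal weighting does.** Let p and q be the observed shares augmented and smoking, with coefficients β_A and β_S. The equal-weight mean equals the observed-mix mean plus (0.5 − p)β_A + (0.5 − q)β_S. If the two factors are independent, the variance ratio is

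1 + k[(0.5 − p)²/(p(1 − p)) + (0.5 − q)²/(q(1 − q))].

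For a Week-12-only ANCOVA, k = 1. In the SAP's model each covariate has one coefficient shared by three visits. With exchangeable r = 0.5, the residual correlation after baseline adjustment is (0.5 − 0.25)/(1 − 0.25) = 1/3, so k = (1 + 2/3)/3 = 5/9.

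**3. Augmentation share.** SAP 3.5.3 quotes 85% power for a fall of 0.42 − 0.38 = 0.04 at SD 0.06, and about 50% at the original SD (printed as 0.9, read here as 0.09). Paired-t power at n = 22 is 84.6% and 51.2%. So about 22 of 30 augmented (73%) is implied, though not stated.

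**4. Size.** Smoking splits are assumptions. At p = 22/30 the term is 0.0544/0.1956 = 0.278. At 20/30 it is 0.125, and at 24/30 it is 0.5625. Power is from simulated trials of n = 30 using individual percent change, a 15% fall at all three visits, no covariate effects, no missing data, and a GLS approximation to the MMRM with 25 df.

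| Augmented / smoking (of 30) | Sum of terms | SE factor, k = 5/9 | Simulated SE rise | Power, equal weights |
|---|---|---|---|---|
| 15 / 15 | 0 | 1.00 | 0% | about 95% |
| 22 / 15 | 0.278 | 1.07 | 7% | about 93% |
| 22 / 20 | 0.403 | 1.11 | 10% | about 91% |
| 22 / 24 | 0.841 | 1.21 | 21% | about 87% |
| 24 / 24 | 1.125 | 1.27 | 27% | about 83% |

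At the observed mix, power is about 95% in every row. These powers move by one to three points with the way the residual variance is estimated; the last row ranges from 82% to 86%.

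**5. Shift in the estimate.** Suppose the fall is 15% without augmentation and 10% with it (an assumption), with 22 of 30 augmented. The treated arm's mean is (8 × 15 + 22 × 10)/30 = 11.3%. The equal-weight mean is (15 + 10)/2 = 12.5%, a difference of 1.2 points. If the SAP's 0.42 to 0.38 (9.5%) is used for the augmented, the figures are 11.0% and 12.3%.

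**6. Outputs affected.** PDIFF in this statement compares visits. Augmentation and smoking have no visit interaction, so their weights cancel there. Only the LS mean, its standard error and its test against zero are affected, and that test is the primary one.

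**The case against.** The strongest reply is that the loss is modest and rests on splits that nobody has stated. The inferred 22 could be 22 of the 33 randomized per arm (67%). Protocol 10.1's 80% power for the same comparison points to n = 20 if SD 0.06 is assumed, which is also 67% of 30. At 20/30 augmented and 15/30 smoking, the standard error rises only 3% and power is about 93.7%. This stands: at the implied augmentation share, power falls below 90% only if smoking is also markedly lopsided.

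A reader might apply the ANCOVA formula (k = 1), which gives rises of about 13%, 18%, 36% and 46% for the four uneven rows. SAP 10 replaced that analysis, so those larger losses do not apply.

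It can also be said that planning on a simpler test is ordinary practice, that equal weighting is a recognised default which holds the reference mix fixed across arms, and that the subgroup analyses and raw summaries in SAP 6.3 and 8 show the effect by augmentation and at the observed mix. The first point stands. The second is a real merit, but pooled margins provide it too. The third helps interpretation but leaves the primary estimate and test as coded.

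**Conclusion.** The code as printed tests a Week 12 mean for a 50:50 augmented and 50:50 smoking arm. The consequence depends on the splits. It is nil at 50:50. At about 22/30 augmented, the standard error rises 7% to 21% and power is about 93% to 87% over the assumed smoking splits, against about 95% at the observed mix. At 24/30 in both factors, power is about 83%. A difference in effect by augmentation would add a shift of about 1 point. These figures assume the SAP's planning inputs, independence of the two factors and complete data.

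A reader might infer that the stated power is wrong or that the trial is underpowered. The documents do not support either: the figure is for an unadjusted paired t-test, where power is 98.4%, and no augmentation or smoking split is given from which a shortfall could be established. The defect is an unstated and probably unintended reference mix for the primary estimate.

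**What to change.** State in SAP 8.1 that the primary test is the Week 12 LS mean in the MPH966 arm against zero, with its 95% confidence interval, evaluated at the observed subject-level mix of augmentation and smoking. Either of these does it:
- Enter augmentation and smoking as 0/1 covariates centred at their subject-level means, take them out of CLASS, and request the LS means with CL, holding both at zero through AT.
- Keep the CLASS effects and use LSMEANS with CL and OM= a margin data set that has one row per subject (repeated for each visit if the procedure needs all visit levels). Plain OM is not enough, because it weights by records and so counts patients with missed visits less.

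The CL option is needed in any case, since the printed statement requests no interval.

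The cost is a few lines of code and one sentence, with no new data. The one downside is that arm-specific margins make the active and placebo means refer to slightly different mixes. Pooled subject-level margins for both arms avoid this. The SAP should name its choice before the blind is broken.

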# 8.2 Secondary Efficacy Endpoint Analyses:

Percent change from baseline in the following outcomes at end of the treatment within patient and compared to placebo:

- 1. Plasma desmosine/isodesmosine (only relative change compared to placebo; within-individual change is the primary outcome)
- 2. Plasma Aa-Val-360
- 3. Serum NE activity
- 4. Plasma proteinase 3
- 5. Plasma cathepsin B
- 6. Plasma CRP
- 7. Plasma IL-6
- 8. Plasma IL-8
- 9. Plasma IL-1b

Plasma RANTES
 Plasma LTB4
 Plasma MMP9
 Plasma MMP12
 Plasma MPO
 Plasma PGP
 Plasma PK/PD (LCG/DDS)

The same approach, i.e., mixed modelling, will be used to analyse the change from baseline within and between treatments for the secondary outcomes using available data based on the schedule of collection and analyses. The analysis will be conducted using the SAS 'proc mixed', with the specific code given below. For each outcome, p-value<0.05 for pairwise comparisons of the least squared means between treatment groups will indicate treatment effect. This will be done for each outcome.

proc mixed data=Data; class SUBJID TRTP AVISIT SMOKING; model PCTCHG = BASE TRT|AVISIT FEV1 AGE SMOKING; ddfm=KENWARDROGER; repeated AVISIT/ subject=SUBJID type=UN; lsmeans TRTP\*AVISIT / pdiff; run;

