#### 10.3.1. Efficacy Analyses

Endpoint	Statistical Analysis Methods
Primary	Within individual % change from baseline in plasma desmosine/isodesmosine levels at 12 weeks will be calculated. An analysis of covariance (ANCOVA) model with baseline plasma desmosine/isodesmosine levels as a covariate and treatment and sputum strata as factors will be used to generate least squared means and least squared mean differences between treatment groups.
Secondary	The biomarker correlation analysis will be done using stepwise approach: The parameters in BAL, sputum, and blood during treatment will be compared to the baseline values for active and placebo patients separately to evaluate natural variability of the markers.  The time-matched biomarker values will be compared between placebo and active groups to assess the differences outside natural variability and time to significant change for the responsive biomarkers.

Endpoint	Statistical Analysis Methods
	
Multiple models, including non-parametric models, will be considered within this frame incorporating different covariates and data transformations. PD parameters such as area under the effect-time curve will also be considered.
 
Principal component multifactorial analysis and/or cluster analysis may be employed to simplify the comparison and to explore the treatment effect. Decisions will be made on review of data and prior to database lock.
 
Correlation of select biomarkers shown to be responsive to treatment with time-matched drug concentrations and PK parameters, if available, may be used to evaluate exposure-response relationship.

Exploratory	
Observed values and change from baseline in FEV1, FVC, FEV1/FVC (total and percent predicted) and maximal mid-expiratory flow will be presented by treatment group and study visit. Change from baseline at Week 12 will be analysed using an ANCOVA model.
 
Observed values and change from baseline for the total and component scores of the SGRQ-C will be presented by treatment group and study visit. Change from baseline in total score at Week 12 will be analysed using an ANCOVA model.
 
Correlation of select biomarkers shown to be responsive to treatment with time-matched drug concentrations and PK parameters, if available, will be used to evaluate exposure-response relationship.

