Biomarker data are reported as concentration results, measured using a specific assay with a working range defined by the two limits: Lower limit of quantification (LLOQ) and Upper limit of quantification (ULOQ). Values which fall below the LLOQ or above the ULOQ are reported as <LLOQ \* dilution factor (dilution factor: if sample diluted and concentration measured still below LLOQ) and > ULOQ \* dilution factor, respectively. All results for the above biomarker parameters, if collected, will be summarised on the respective populations by descriptive statistics stratified by treatment and time-point, and including the geometric mean and coefficient of variation. Changes in the biomarker concentrations from baseline (Study Day 1 pre-dose) will be also summarised at each post-baseline time-point. In the summary table, the frequency (n, %) of values below the LLOQ and above the ULOQ, respectively, will be included. In case of values below the LLOQ and/or values above the ULOQ, the values, reported as <LLOQ will be imputed as 0.5\*LLOQ and values reported as >ULOQ will be imputed as 1.5\*ULOQ.

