# 8 Efficacy Analyses

Analyses on all efficacy outcomes will be based on the 12-week period after randomization. Time periods included are baseline, Week 4, Week 8 and Week 12. Safety outcomes will include through Week 16.

Actual values, absolute change in actual values and the relative (percent) change from baseline will be summarised with descriptive statistics for continuous variables overall and by treatment arms. Relative (percentage) change will be calculated by:

[(Week or EndPoint value – Baseline Value) / Baseline value)] x 100%.

Baseline value will be computed as the last non-missing value prior to first study treatment dose at baseline visit (V1).

EndPoint will be computed as:

- Value at Week 12 for the completers (regardless of treatment compliance) or
- EOT value must be last non-missing post-baseline value for those that discontinue treatment before Week 12.

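### SAP 8.2 models arithmetic percent change for 14 non-DES blood biomarkers and names no log-ratio model; if these markers are skewed, within-arm results mislead and between-arm power is lost

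*SAP*

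**What the plan says.** SAP 8.2 lists 16 secondary outcomes and sets the response as "Percent change from baseline in the following outcomes at end of the treatment within patient and compared to placebo". Without DES (item 1) and the PK/PD item (item 16), 14 blood biomarkers remain: Aα-Val-360, NE activity, proteinase 3, cathepsin B, CRP, IL-6, IL-8, IL-1b, RANTES, LTB4, MMP9, MMP12, MPO and PGP. SAP section 8 defines relative change arithmetically, as follow-up minus baseline, divided by baseline, times 100. The code in 8.2 is "model PCTCHG = BASE TRT|AVISIT FEV1 AGE SMOKING": raw percent change on raw baseline with no log step. Both directions of inference are planned: "The same approach, i.e., mixed modelling, will be used to analyse the change from baseline within and between treatments for the secondary outcomes". The decision rule is between arms: "p-value<0.05 for pairwise comparisons of the least squared means between treatment groups will indicate treatment effect".

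On distribution, SAP 8.1 says "Transformation of data or alternative distribution for the model will be considered should there be evidence of nonnormality of the data", and 8.2 inherits this by taking the same approach. Protocol 10.3.1 is equally open for the secondary biomarkers: "Multiple models, including non-parametric models, will be considered within this frame incorporating different covariates and data transformations". Neither names a scale, a test or a trigger. SAP 6.1 adds further biomarker summaries, "including the geometric mean and coefficient of variation", and imputes results below the LLOQ at half the LLOQ.

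**The concern.** A percent change has the baseline as its denominator. When a marker varies widely between and within patients, a low baseline tends to be followed by a higher value, and the ratio is then very large. A high baseline followed by a low value can never fall below −100%. The arithmetic mean of percent change is therefore positive even when the distribution of the marker has not moved, and its spread is inflated by a few large ratios.

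Three things are at stake.

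- Within-arm estimates can show increases where nothing happened and can hide real falls. Protocol 10.3.1 uses comparisons with baseline in each arm separately to judge natural variability, which is where the effect is largest.
- The between-arm test loses power. SAP 8.3 and 8.5 carry forward only responsive or significant biomarkers to the exposure-response work, so a missed signal is missed twice.
- A scale chosen marker by marker after seeing the data adds analyst freedom across 14 unadjusted tests.

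A log cannot simply be applied to the specified response, because percent change takes negative values. The response itself has to be redefined as a log ratio, and neither document says so.

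**Working it through.** **The plan's own figure.** The documents give no power or SD for the 14 markers; only DES has both a variability figure and a correlation (SAP 3.5.3: mean 0.466, SD 0.09, correlation 0.5). For the paired test, the difference is 0.15 × 0.466 = 0.0699 and the SD of change is 0.09 × √(2 × (1 − 0.5)) = 0.09. With n = 30 and two-sided 5%, noncentral-t power is 98.4%, which agrees with the stated >90%.

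**Assumptions for the other markers.** Lognormal; CV 0.5 to 1.0 or log-SD up to 1.0; log-scale correlation r of 0.5 or 0.7; 30 per arm; true falls of 30% or 50%. None of these comes from the documents, except the 30 per arm and the r of 0.5 borrowed from DES. One post-baseline visit is apt, because SAP Table 1 schedules 12 of the 14 markers at a single post-baseline visit (Week 12).

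**Mean percent change with no true effect.** With σ² = ln(1 + CV²), this is exp(σ²(1 − r)) − 1. For DES: CV = 0.09/0.466 = 0.193, σ² = ln(1.0373) = 0.0366, exp(0.0366 × 0.5) − 1 = 1.8%. For CV 0.5 and r 0.7: exp(0.223 × 0.3) − 1 = 6.9%. For log-SD 1.0 and r 0.5: exp(0.5) − 1 = 64.9%.

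| CV (log-SD) | r | Mean % change, no effect | False within-arm increase (nominal 2.5%) |
|---|---|---|---|
| 0.19 (DES) | 0.5 | +1.8% | about 9% |
| 0.5 (0.47) | 0.7 | +6.9% | 14% to 15% |
| 0.5 (0.47) | 0.5 | +11.8% | 23% |
| 1.0 (0.83) | 0.7 | +23.1% | 28% |
| 1.0 (0.83) | 0.5 | +41.4% | 39% |
| (log-SD 1.0) | 0.5 | +64.9% | about 41% |

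The last column is simulated with a baseline-adjusted model; the log-ratio model gives about 3%. An unadjusted one-sample t-test gives slightly lower rates: 20%, 28% and 37% at log-SD 0.6, 0.8 and 1.0 with r = 0.5.

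**Between-arm power.** Simulated ANCOVA, 30 per arm, r = 0.5: percent change on baseline against log ratio on log baseline.

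| Variability | True fall | Percent change | Log ratio |
|---|---|---|---|
| CV 0.19 (DES) | 15% | 95.2% | 95.9% |
| CV 0.5 | 30% | 85.2% | 91.0% |
| log-SD 0.6 | 30% | 62% | 74% |
| CV 1.0 | 30% | 31.6% | 46.4% |
| CV 1.0 | 50% | 80.8% | 95.2% |
| log-SD 1.0 | 50% | 59% | 85% |

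The largest loss in this range is 85 − 59 = 26 points. The smallest for a 30% fall, about 1 point, is at CV 0.5 and r 0.7, where both models are near full power. At CV 1.0 and a 30% fall, about 80% power needs roughly 110 per arm on percent change and 65 on the log ratio. Within-arm power falls further: 44% against about 88% (30% fall, log-SD 0.6), and about 33% against 95% (50% fall, log-SD 1.0).

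**Between-arm type I error.** On percent change it stays between 3.9% and 5.1%.

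**How a real effect would read.** At CV 1.0, r 0.5 and a true 30% fall, the placebo mean is +41.4% and the active mean is 0.70 × 1.414 − 1 = −1.0%. The contrast is 0.990 − 1.414, or −42 points. A working drug would look flat beside a worsening placebo arm, and the size of the contrast depends on the marker's noise as well as on the drug.

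**Limits.** Lognormal shape, one visit, no age, smoking or FEV1 terms, no missing data. The within-arm log test itself rejects 6% to 7% in total, because the baseline mean is treated as fixed.

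**The case against.** The strongest reply is that the size of the problem is assumed. The documents give no SD, CV, correlation or distribution for any of the 14 markers, and at the one CV they do support, that of DES, the shift is under 2 points and the between-arm power loss under 1 point. This stands, and the figures above are illustrations over a stated range.

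Second, a fallback exists. SAP 8.1 and Protocol 10.3.1 both foresee transformation, and the markers with the largest spread are the ones where non-normality would be seen. Nothing says the check would be made unblinded. This softens the point but does not remove it: no scale, trigger or redefined response is named, and SAP 6.1 places all analyses after data lock.

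Third, percent change is not the only scale. The table list in SAP 14.1 has absolute as well as relative change for all of these markers except PGP, and 6.1 adds medians and quartiles. A spurious percent increase would sit beside an absolute change centred on zero. That helps a careful reader, but the models in 8.2 are written for percent change.

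Some stronger readings are tempting and are not supported:

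- A reader might infer from the geometric means in SAP 6.1 that the plan already treats these markers as lognormal. It does not say so, and the only CV formula it gives (8.5.1.2, for PK) is the arithmetic one.
- A reader might infer a risk of false efficacy claims. The decision rule is between arms, where type I error is not inflated, and the within-arm artefact is an increase, against the hoped-for direction.
- A reader might call the estimates biased outright. The model is unbiased for the arithmetic mean percent change. The shift is relative to no change in distribution, or to the geometric-mean ratio.
- A reader might extend the point to the primary analysis. DES within-arm power is 98% on percent change and 99.5% on the log scale, so there is little to gain.

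**Conclusion.** The point holds in a conditional form. SAP 8.2 does specify arithmetic percent change on raw baseline for 14 non-DES markers, and the provision for transformation is too loose to count as a plan. The harm rests on the lognormal assumption with CV of 0.5 or more; for markers as stable as DES it is negligible. Under that assumption it consists of misleading within-arm means and tests, an effect size that is hard to interpret, and lost power in the comparison that decides each marker. It concerns unadjusted, signal-seeking secondary tests and does not threaten the primary endpoint. The change is worth making because the log-ratio model gains up to about 26 points of power where markers are skewed and loses almost nothing where they are not.

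**What to change.** Before unblinding, amend SAP 8.2 for the 14 non-DES concentration biomarkers:

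- Model log(post/baseline) with log(baseline) as covariate in place of PCTCHG on BASE, keeping the other terms of the mixed model.
- Report exp(LS mean) − 1 in each arm, as percent change in geometric mean, and the between-arm geometric-mean ratio, each with a 95% CI.
- Keep arithmetic percent change as a descriptive summary.
- Leave DES on its percent-change scale, and add a log-ratio analysis of DES as a sensitivity analysis only.
- Say how markers with many values imputed at half the LLOQ will be handled. Such values are unstable as the denominator of a percent change and also distort a log ratio, so they need care on either scale.

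The cost is a few lines of SAP text and one data step. The small downside is that results are geometric-mean ratios rather than mean percent changes.
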